assessed using a standard, validated and tested tool—the visual analog scale (VAS) and quality of recovery (QoR) questionnaire respectively. Patients will be asked to assess their pain level and recovery status using VAS and QoR questionnaires respectively at standard time points: 1 hr (+/- 20 minutes), 3 hrs (+/- 20 minutes), and 5 hrs (+/- 20 minutes) postoperatively, and then asked for their maximal pain level everyday during waking hours from 7 am to 9 pm until the day of discharge.

Once discharged, patients will be asked to assess their pain level and quality of recovery everyday via a telephone call everyday between 7 am to 9 pm until their first follow-up appointment at 1 week postoperatively. Patients will be seen at 1 week (+/- 4 days) and 3 weeks (+/- 7 days) post operatively and asked to assess their pain level and recovery status using VAS and QoR questionnaires.

Data collection will include patient factors such as demographics, comorbidities, smoking status, operative factors including number of lymph nodes taken (if any), intraoperative analgesia consumption, type of mastectomy and reconstruction, type and size of expander, and postoperative factors such as opioid and narcotic use, nausea/vomiting, time to discharge, pain level using the visual analog scale (VAS) and recovery status using quality of recovery (QoR) questionnaire.

Primary outcome will be the rate of reduction of postoperative pain as quantified by VAS.

STATISTICAL PROCEDURES

Using our previous placebo-controlled study for the effect of PEMF [6] and prior literature comparing placebo to PIB [5], we determined that a sample size of 48 (12 per group) was necessary to ascertain a clinically meaningful difference in pain level with a statistical power of 80%. We plan to enroll 60 patients overall to compensate for dropout. Interim analysis will be performed by unblinded research team members when at least 30 patients have been accrued, completed follow-up visits and are off study. Preliminary analysis before the final data analysis will be performed by unblinded research team members when 51 patients have been accrued, completed follow-up visits and are off study. Final data analyses will be conducted in consultation with a biostatistician who will consult on appropriate tests for evaluating the normality of data and for performing comparative regression analyses of the data.

RECRUITMENT AND CONSENT

RECRUITMENT

Describe how participants will be recruited

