Recruitment will take place during patients' scheduled consultations with the breast surgeon or plastic surgeon. Patients who present for mastectomy will be given the standard discussion of all breast reconstruction options. After this, patients who decide to have tissue expanders placed will be asked to participate in this study. Informed consent will be obtained. Throughout this, patients will be given opportunities to ask questions at any time during the enrollment and study and will be informed that they can decline to participate or drop out of the study at any time. After the informed consent is signed, the patient will be randomized into one of 4 groups—placebo (sham PEMF + sham PIB), active PEMF +sham PIB, PIB + sham PEMF, or active PEMF and PIB (Table 1).

RESEARCH AIMS AND ABSTRACTS

RESEARCH QUESTION(S)/HYPOTHESIS(ES)

Aim 1: To quantify the effect of PEMF devices on postoperative pain in mastectomy + tissue expander patients

Rationale: Prior studies have demonstrated the ability of PEMF devices to afford a significant reduction in postoperative pain for patients undergoing breast reduction or TRAM flap breast reconstruction. The proposed study seeks to establish whether PEMF is similarly efficacious in reducing postoperative pain in mastectomy + tissue expander patients.

Hypothesis: Mastectomy + tissue expander patients randomized to an active PEMF device and sham PIB will have significantly decreased postoperative pain as measured by VAS score compared to the sham PEMF and sham PIB group.

Aim 2: To evaluate the effect on PEMF devices on postoperative narcotic requirements

Rationale: In our previous double-blind, placebo-controlled, clinical study in breast reduction patients, we reported a two fold decrease in the use of postoperative narcotics when PEMF devices were used. As increased narcotic usage can have a host of side effects and delay healing, the proposed study seeks to evaluate the ability of PEMF devices to reduce postoperative narcotic requirements in mastectomy + tissue expander patients.

Hypothesis: Patients undergoing mastectomy + tissue expander placement randomized to active PEMF and sham PIB will have significantly reduced postoperative narcotic requirements as compared to the group randomized to sham PEMF and sham PIB.

Aim 3: To compare the efficacy of PEMF vs. PIB in the control of post-operative pain in mastectomy + tissue expander patients.

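### The primary VAS outcome has no start, end or formula and does not match the between-arm pain level in Aims 1 and 3; computed as absolute change or slope from the first score, it removes any effect already present at 1 h

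*Combined protocol and SAP*

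**What the plan says.** The RANDOMIZATION section, just before STATISTICAL PROCEDURES, states: "Primary outcome will be the rate of reduction of postoperative pain as quantified by VAS". The SCIENTIFIC ABSTRACT and LAY ABSTRACT instead make the primary outcome a reduction in VAS pain level, compared across the four groups, with no mention of a rate.

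The same part of the RANDOMIZATION section schedules VAS at "1 hr (+/- 20 minutes), 3 hrs (+/- 20 minutes), and 5 hrs (+/- 20 minutes) postoperatively". Patients are "then asked for their maximal pain level everyday during waking hours from 7 am to 9 pm until the day of discharge". After discharge there are daily telephone assessments up to the first follow-up visit, and "Patients will be seen at 1 week (+/- 4 days) and 3 weeks (+/- 7 days) post operatively". The calls and visits ask for pain level and are not said to ask for the maximum. No preoperative VAS is listed.

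The Aim 1 and Aim 3 hypotheses predict lower VAS pain in one arm than in another. The Aim 3 hypothesis describes the block as a single injection before surgery and the device as worn for 7 days after it. STATISTICAL PROCEDURES says that 48 patients (12 per group) are "necessary to ascertain a clinically meaningful difference in pain level" with 80% power. It plans two unblinded analyses before the final one: "Interim analysis will be performed by unblinded research team members when at least 30 patients have been accrued" and "Preliminary analysis before the final data analysis will be performed by unblinded research team members when 51 patients have been accrued". The final methods are left to consultation with a biostatistician.

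**The concern.** Two defects follow from the text alone. First, the primary outcome cannot be computed as written, because several variables fit the wording and nothing selects one. Second, a within-patient rate of decline is a different quantity from the between-arm pain level that the hypotheses and the sample-size sentence concern.

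A third problem is conditional. With no earlier VAS listed, a natural way to compute a reduction or its rate is from the 1 h score. That score is taken after the block, so for any block contrast it is itself an outcome of treatment. Using it as a starting point subtracts part of the effect under study. A treatment that lowers pain early could then show no advantage, or look worse than sham.

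The plan also does not fix the definition before unblinded team members analyse data at 30 and 51 patients.

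**Working it through.** **1. The plan's own figure.** The 12 per group cannot be reproduced, because significance level, sidedness, effect size, SD and test are not given. Back-solved at two-sided 5% and 80% power, it corresponds to a difference of √(2/12) × (1.960 + 0.842) = 1.14 SD (normal approximation), or 1.20 SD with a t-test. The 60 enrolled matches 48/(1 − 0.20) = 60, where the 20% is implied. The sentence refers to a difference in level, so it gives no help in defining a rate.

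**2. Candidate start and end points.** The only listed start candidates are postoperative, the first at 1 h. The end could be discharge, the 1-week visit (7 ± 4, day 3 to 11) or the 3-week visit (21 ± 7, day 14 to 28). If the rate is points per day, an assumed 3-point fall to the 1-week visit is 3/3 = 1.0 per day on day 3 and 3/11 = 0.27 on day 11, both inside the window.

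**3. Change from 1 h.** Let B(t) be mean VAS in the comparator minus mean VAS in the treated arm at time t. The difference between arms in reduction from 1 h to a later time T is

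[treated(1 h) − treated(T)] − [comparator(1 h) − comparator(T)] = B(T) − B(1 h).

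- Constant benefit: B(T) = B(1 h), so the result is 0. A fitted slope is likewise unchanged by a constant shift.
- Benefit gone by T: the result is −B(1 h), so the treated arm scores as worse.
- No effect at 1 h: the result is B(T), the late level difference.

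Percent change follows different algebra: a constant proportional benefit cancels, but a constant absolute one does not.

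**4. Consequence for Aim 3 (illustration only).** If late pain is equal, the PEMF-versus-PIB difference in change equals the difference d between their 1 h effects, in favour of the treatment with the smaller one. The documents give no SD, correlation or effect size. Assumed: VAS SD 2 to 2.5, correlation ρ of 0 to 0.7 between the two scores, 15 per arm, two-sided 5%.

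SD of change = SD × √(2(1 − ρ)); noncentrality = d / (SD of change × √(2/15)); 28 degrees of freedom; critical t 2.048.

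| Setting | SD of change | d = 1: noncentrality, probability | d = 2: noncentrality, probability |
|---|---|---|---|
| SD 2.5, ρ 0 | 3.54 | 0.77, 11% | 1.55, 32% |
| SD 2, ρ 0.7 | 1.55 | 1.77, 40% | 3.54, 93% |

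These are the extremes of the grid. The probability is that the arm with the smaller 1 h effect is declared better. With d = 0 it is 2.5%. With 12 per arm the ranges are 10-33% and 26-86%.

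**5. Consequence for Aim 1 (illustration only).** Assumed: 12 per arm, a late effect of 1.144 SD (80% power on level), ρ 0.5 (so the SD of change equals the SD), normal approximation. If a fraction f of the late effect is already present at 1 h, power on change is Φ(1.144(1 − f)/√(2/12) − 1.96):

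| f | 0 | 0.25 | 0.50 | 0.75 | 1 |
|---|---|---|---|---|---|
| Power | 80% | 56% | 29% | 10% | 2.5% |

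The documents give neither f nor the time at which the device is switched on.

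**The case against.** The strongest reply is that reduction need not mean within-patient change. The Aim 1 rationale says earlier studies showed that PEMF can "afford a significant reduction in postoperative pain for patients undergoing breast reduction", and POTENTIAL BENEFITS uses the word in the same way: less pain than without the treatment. On that reading the abstracts agree with the aims, and nothing cancels or reverses. No section calls the 1 h score a baseline. This stands, and it makes the loss conditional. It does not rescue the word rate, and it leaves the summary measure and time window open.

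A second reply concerns Aim 1. Both arms of that contrast receive the sham block, so the block's timing is irrelevant to it. If PEMF has no effect at 1 h, change from 1 h estimates the late level difference. This also stands. A reader might infer that the stated outcome fails to test Aim 1 at all; the documents do not support that.

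Third, the percentages rest on assumed inputs, and patient-controlled analgesia in all arms for the first 24 hours could narrow the 1 h difference. That is a fair limit on their size, not on the algebra.

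Finally, a trajectory outcome could be legitimate if prespecified, given the 7-day-versus-single-injection rationale of Aim 3. But the Aim 3 hypothesis is worded as pain level, and no trajectory is specified.

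**Conclusion.** The point holds and needs correcting before analysis. It is certain from the text that the primary outcome has no start, end or formula, that its wording differs between sections, and that a within-patient rate is not the between-arm level in Aims 1 and 3 and the sample-size sentence.

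It is conditional that effects are lost or reversed. This follows if the outcome is absolute change or slope from 1 h, and its size depends on the effect present at 1 h. It bears mainly on Aim 3 and other block contrasts. On the assumptions shown, a false declaration in favour of the arm with the smaller 1 h effect occurs in 11-40% of trials for a 1-point difference and 32-93% for 2 points, against 2.5% for none. These figures illustrate the mechanism; they are not estimates for this trial.

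Two further inferences are not supported. A reader might conclude that the Aim 3 comparison is tilted towards PEMF; neither 1 h effect is given, so the direction is unknown. A reader might also conclude that the definition will be picked after an unblinded look; no section says so, only that nothing prevents it.

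**What to change.** - Replace the rate of reduction with VAS level compared between randomised arms over one postoperative window fixed in advance, either as a time-weighted mean or from a repeated-measures model. Do not use the 1 h score as a baseline.
- State which scores enter the outcome, distinguishing three sets: the 1, 3 and 5 h scores; the inpatient daily maximal scores; and the post-discharge call and visit scores, which are not stated to be maximal.
- Report any reduction or slope as secondary, with its start, end and formula.
- Align the outcome sentence in the RANDOMIZATION section and both abstracts with Aims 1 and 3.
- Date the change before any further unblinded look and disclose any look already made. In that case report the reduction-based result alongside.

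The cost is a dated change to Version 6, with no additional patients or VAS assessments. There are two downsides. A long window dilutes a short early effect, so the investigators must choose the window knowingly. A change made after an unblinded look may be seen as data-driven, which is why its timing must be disclosed.

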Describe the methodology that will be used in this study, covering such factors as retrospective vs. prospective data collection, interventional vs. non-interventional, randomized vs. non-randomized, observational, experimental, ethnography, etc.

We propose a prospective randomized controlled double-blind interventional study comparing the effect of pulsed-electromagnetic field device (PEMF), pectoral interfascial block (PIB), and placebo on postoperative pain control. This study has the interdisciplinary cooperation of the regional anesthesia group, and the breast and plastic surgery divisions. All female patients with breast cancer evaluated at CUMC who are undergoing unilateral or bilateral mastectomy with tissue expander reconstruction will be offered enrollment in this prospective study. Patients must be 18 years of age or older. Exclusion criteria include patients who are allergic to all narcotic medications, those who take opioids or pain medications for a chronic condition or chronic use preoperatively and medical record specifically states the chronic condition, and those who do not possess the capacity to make medical decisions for themselves.

Version 6

29 June 2021

RANDOMIZATION

The surgeons, all health-care personnel involved in the trial, the research coordinator, and all patients will be blinded. We have identified two volunteers who are not involved in the study in any way and share a locked office. This guarantees that a volunteer will be available on the day of surgery. They will create randomization envelopes based on the following randomization scheme:

Active PEMF + Treatment PIB	Active PEMF + Sham PIB
Sham PEMF + Treatment PIB	Sham PEMF + Sham PIB

The volunteers will:

- Create a randomization list with four arms (15 subjects in each arm) using this link: <https://www.random.org/lists>
- Create 60 sequential envelopes and place a paper with the assignment based on the randomization list.

The sequential randomization envelopes will be kept in the volunteer's locked office. Bupivacaine/Ropivacaine will be stored in the NYPH 4th Floor Pharmacy. On procedure day:

- One of the volunteers will retrieve a sequentially numbered and sealed randomization envelope and will retrieve the study drug from the NYPH pharmacy and hand it to the study physician;

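### The primary VAS summary and model are not fixed before unblinded team members analyse the data at 30 and 51 of 60 patients, so the final method can be chosen with results by arm in view

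*Combined protocol and SAP*

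**What the plan says.** The analysis plan is one paragraph under Statistical Procedures. It gives a sample size ("we determined that a sample size of 48 (12 per group) was necessary"), an allowance for losses ("We plan to enroll 60 patients overall to compensate for dropout"), two analyses before the end, and a closing sentence on the final analysis.

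- **First analysis:** by unblinded team members, once at least 30 patients have finished follow-up.
- **Second analysis:** "Preliminary analysis before the final data analysis will be performed by unblinded research team members when 51 patients have been accrued", again with follow-up complete.
- **Final analysis:** a biostatistician is brought in at this stage, and the task set is to "consult on appropriate tests for evaluating the normality of data and for performing comparative regression analyses of the data".

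No test, model, covariate, significance level or rule for repeated or missing scores is named.

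The primary outcome is described in different ways. The end of Study Design makes it the rate at which VAS pain falls. The scientific and lay abstracts make it the reduction in pain level. The Aim 1 hypothesis speaks of active PEMF patients who "will have significantly decreased postoperative pain as measured by VAS score compared to the sham PEMF and sham PIB group", which reads as a comparison of levels. None of these comes with a formula.

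Study Design collects VAS at 1, 3 and 5 hours, daily until the first follow-up visit at about one week, and at the one-week and three-week visits. It does not say which scores enter the primary analysis.

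**The concern.** The order of events is the plan's own: results by arm are produced twice, and the method for the primary comparison is settled afterwards. Several VAS summaries and several tests would all comply with the text. Someone who knows which of them favours which arm could choose accordingly, deliberately or not, and a reader of the final report could not rule that out.

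This is separate from the question of alpha at the two earlier analyses. Suppose no efficacy claim were allowed at 30 or 51 patients. The final p-value would still come from a method chosen after results by arm were available, and spending alpha across the looks would not cure that.

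**Working it through.** **The plan's own figure.** The 48 evaluable patients cannot be reproduced, because the difference, SD, significance level and test are not given. Only the enrolment figure can be matched: 48 / (1 - 0.20) = 60, with 20% dropout as an assumption. The sample-size statement therefore does not reveal which VAS summary or test was intended.

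**How much is known before the method is chosen.** The second analysis covers 51/60 = 85% of patients. If information is proportional to patients, a given test statistic at 51 has correlation sqrt(51/60) = 0.92 with the same statistic at 60. At 30 patients the correlation is sqrt(30/60) = 0.71. The ranking of candidate methods at 51 patients is thus a good guide to their ranking at the end.

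**How much room the choice gives.** Inputs from the documents:
- 15 patients per arm
- VAS at 1, 3 and 5 hours, then daily to about one week

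Assumptions:
- ten scores per patient (three early, seven daily)
- normal scores with equal correlation of 0.3, 0.5 or 0.7 within a patient
- no treatment effect
- two-sided 5% level
- the smallest p-value always taken

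The four summaries are the mean of all ten scores, the slope on time, the mean of the 1, 3 and 5 hour scores, and the day-7 score. The false-positive rate is the share of simulated trials in which the smallest p-value on the menu is below 0.05. The ranges below cover three separate sets of runs (3,000, 6,000 and 20,000 per correlation). The single-test row comes from the sets of 3,000 and 20,000.

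| Menu | False positives |
|---|---|
| One fixed t-test on the mean score | 4.7-5.4% |
| Better of t-test and rank test on the mean score | 5.5-6.1% |
| The above, plus slope | 10.0-10.9% |
| The above, plus early mean and day-7 score | 12.9-16.3% |

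**Which choice matters.** In the 20,000-run set, the t-test alone across the four summaries, with no choice of test, already gives 13.2-15.1%. The step from one test to two on a single summary adds about one percentage point. The choice of VAS summary carries most of the inflation.

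**The normality test taken alone.** If a normality test did decide between a t-test and a rank test on one fixed summary, simulated type I error is 5.1-5.7%, which is close to nominal.

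**Dependence on the menu.** Another plausible menu uses 11 scores, with first-minus-last, hour-1-minus-day-7, slope and mean, each by t-test and rank test. It gives about 19%. The 13-16% is an upper bound for the menu shown, not for every menu the text would allow.

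**The case against.** The strongest reply is that the plan has no stated defect of method. A biostatistician will be consulted, regression is named, and nothing says that this person is unblinded or took part in the earlier analyses. The percentages assume that the most favourable result is always picked, which no one has proposed. Both points stand. The figures describe what the text permits and do not predict conduct. They do not remove the gap, because no section says that the method is fixed before the looks or that those who choose it are kept from results by arm.

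Two further inferences are tempting, and the documents do not support them.

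- **That normality tests within arms of 12 to 15 patients will steer the method.** The text lists normality tests and regression as two subjects of consultation. It does not say that one decides the other, nor whether normality would be examined by arm or on pooled residuals. Even as a gate, such a test does little harm, as the 5.1-5.7% shows.
- **That the repeated scores will be wasted, at a cost in precision.** The plan nowhere proposes a comparison at a single time, and a regression can be longitudinal. A gain from averaging would apply only to a time-averaged VAS set against a single score, under assumed correlations. It does not carry over directly to a rate of reduction.

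**Conclusion.** The concern holds in this form: the primary VAS summary, time points and model are open until the final analysis, after results by arm have been produced at 50% and 85% of enrolment. The nominal error rate is therefore not protected, whatever is decided about claims at those looks.

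The possible size, as an upper bound for the menu examined, is about 6% if only the test is chosen and about 13 to 16% if the VAS summary is chosen as well, against a nominal 5%. This rests on an assumed two-sided 5% level, ten scores per patient, normal scores, equal correlation of 0.3 to 0.7, and always taking the best result. The absence of a fixed method and the order of the analyses rest on the text alone.

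The change should be made. It is cheap and needs no new data.

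**What to change.** Before any further unblinded output is produced, have a biostatistician who has not seen results by arm sign a dated SAP that does three things.

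1. **Defines the target.** State one primary VAS summary, its time window, and the exact contrasts. For Aim 1, compare active PEMF with sham PIB against double sham. For Aim 3, compare active PEMF with sham PIB against sham PEMF with treatment PIB. If the rate of reduction is kept, the contrast could be the between-arm difference in change per day; if not, the difference in time-averaged VAS. Use the same definition in Study Design and both abstracts.
2. **Names one model.** Estimate those contrasts from a linear mixed model on all VAS scores in the window, from every randomised patient with at least one score. Include arm, time and arm x time, allow for within-patient correlation, and use small-sample degrees of freedom. State how time enters, since a slope contrast depends on it.
3. **Closes the remaining choice.** Say that no normality test will change the primary method, and give a re-randomisation (permutation) p-value as the sensitivity analysis.

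Step 1 must come first: a named model with an undefined window or contrast would leave most of the freedom in place.

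The cost is about a page of SAP text and a few hours of biostatistician time moved earlier. The team also gives up the freedom to change the method later. No extra patients, visits or measurements are needed.
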